12.3. Laboratory determinations

Actual values and change from baseline values for continuous data from laboratory determinations will be summarized descriptively by received study drug at all scheduled study visits (Sections 5.1 - 5.3, unless otherwise specified). The laboratory tests is listed in Appendix E.

12.3.1. Transaminases

Evaluation of Drug-Induced Serious Hepatotoxicity (eDISH) plots are generated for ALT and AST versus TBL

The number and percentage of patients meeting the following thresholds, which are consistent with FDA guidance, are summarized by the maximum dosage received:

Table 1: Pre-Specified Threshold Levels for Transaminases

Lab Parameter	Threshold
ALT, AST	$\geq 3 \times$ upper limit of normal (ULN) and $< 5 \times$ ULN
	$\geq 5 \times$ ULN and $< 10 \times$ ULN
	$\geq 10 \times$ ULN and $< 20 \times$ ULN
	$\geq 20 \times$ ULN
	$\geq 5 \times$ ULN for more than 2 weeks
TBL	\geq ULN and $\leq 1.5 \times$ ULN
	$> 1.5 \times$ ULN and $\leq 2 \times$ ULN
	$> 2 \times$ ULN
ALT, /AST, TBL	ALT or AST $> 3 \times$ ULN and Total bilirubin $> 1.5 \times$ ULN
	ALT or AST $> 3 \times$ ULN and Total bilirubin $> 2 \times$ ULN
ALT, AST, TBL, INR	$> 3 \times$ ULN and (TBL $> 2 \times$ ULN or INR > 1.5)

Lab Parameter	Threshold
ALP	$> 1.5 \times \text{ULN}$

A summary table that includes frequencies and percentages of patients that meet any of the above criteria at any time during the study is provided. A listing of subjects with abnormal ALT, AST, or TBL will also be provided.

12.3.2. Line plot and Boxplot presentations

Boxplot figures will present the distribution of laboratory values (both observed and change from baseline) over time by treatment group. Additionally line plots of change from baseline of laboratory values, vital signs and ECG by visit and treatment analysis group will be generated up to and including study week 28.

12.3.3. Shift tables

Clinical laboratory test results categorized as in or out of the limits of the normal range will be summarized using “worst case shift tables,” that is, by cross-tabulating baseline result categories (high, normal, low) with worst case results during the treatment period. Shift tables will not be limited to results collected at scheduled visits, but will use all available results.

In addition, for ALT, AST and TBL, shift table summarizing (1) baseline to end of treatment, (2) baseline to worst on-treatment, (3) baseline to worst off-treatment, and (4) worst on-treatment to worst off-treatment will be presented.

12.4. 12-lead Electrocardiogram

All ECG measurements including ventricular rate, QT interval, Corrected QT interval - Fridericia’s formula (QTcF), and the overall interpretation will be displayed in a data listing. Only QTcF will be summarized. The QTcF will be calculated based on the following formula:

- $QTcF = QT / \text{cube-root}(\text{RR interval})$
- $RR \text{ interval} = 60 / \text{heart rate}$

A summary table of the actual values and change from baseline will be presented for QTcF by treatment group. In addition, the categories for QTcF of: ≤ 450 msec, $> 450 - 480$ msec, $> 480 - 500$ msec, and > 500 msec, and categories of change from baseline for QTcF of: ≥ 30 msec and ≥ 60 msec will be summarized by visit and treatment group.

12.5. Vital signs and weight

Actual values and changes from baseline values for vital signs and weight will be summarized descriptively by treatment group at all scheduled study visits. Vital sign measurements will include blood pressure, heart rate, temperature, and respiratory rate.

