At a minimum, unscheduled visits should include collection of adverse events, clinical chemistry, hematology, concomitant medications and vital signs, as well as collection/review of weight diary. Additional conversations may be necessary with the medical monitor following an unscheduled visit to assess patient safety.

9.8. **Pregnancy**

9.8.1. **Women of Childbearing Potential**

Women of childbearing potential (WOCBP) are those who are not surgically sterile (no history of bilateral tubal ligation, hysterectomy, or bilateral salpingo-oophorectomy) do not have fallopian inserts with confirmed blockage, have not had reproductive potential terminated by radiation, and are not postmenopausal for at least 1 year.

9.8.2. **Methods of Birth Control**

During Screening, while taking study drug and until 30 days following administration of the final dose of study medication, WOCBP must practice one of the following acceptable methods of birth control:

- Use double barrier contraception method defined as male use of a condom and female use of a barrier method (*e.g.*, contraceptive sponge, spermicidal jelly or cream, diaphragm [always use with spermicidal jelly/cream]);
- Use of hormonal contraceptives (oral, parenteral, vaginal, or transdermal) for at least 90 days prior to start of study drug administration;
- Use of an intrauterine device;

- Abstain from sexual intercourse completely. Complete abstinence from sexual intercourse is only acceptable if it is the preferred and usual lifestyle of the individual. Periodic abstinence is not permitted.

During Screening, while taking study drug and until 30 days after the final dose of study medication is taken, males who have female partners of childbearing potential must practice one of the following methods of birth control:

- Have had a vasectomy (at least 6 months earlier);
- Use double barrier contraception method, defined as male use of a condom and female use of a barrier method (*e.g.*, contraceptive sponge, spermicidal jelly or cream, diaphragm [always use with spermicidal jelly/cream]);
- Partner use of an intrauterine device;
- Partner use of hormonal contraceptives (oral, parenteral, vaginal or transdermal) for at least 90 days prior to start of study drug administration;
- Abstain from sexual intercourse completely. Complete abstinence from sexual intercourse is only acceptable if it is the preferred and usual lifestyle of the individual. Periodic abstinence is not permitted.

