5.2.1. Laboratory parameters

Post-baseline laboratory measurements are defined as the scheduled or unscheduled measurements collected closest to (or on) the patient’s target visit day ([Appendix D](#)), with collection date identified in the central laboratory data. If two assessments are equidistant from a

target study day, the earlier assessment is used. If the visit used for analysis includes two assessments on the same day, the average of the two measurements will be used. As with the baseline retest convention, if both the original and a retest result for a scheduled post-baseline laboratory are available in the central laboratory data, the original result will be used and the second (i.e., ‘retested’) result will be ignored. Otherwise, if the original result is not available (e.g., central laboratory detects an error) but a retest result is available, the retested result will be used as the scheduled post-baseline measurement.

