5.2.2. Non-laboratory parameters

Post-baseline measurements of non-laboratory parameters are defined as the measurements collected on the day closest to the patient’s target visit day ([Appendix D](#)). If two assessments are equidistant from a target study day, the earlier assessment is used. If the visit used for analysis includes two assessments on the same day, the average of the two measurements will be used. The last clinic visits on and off study drug will be classified according to when they occurred as specified in [Section 5.2.3](#).

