12.5.1. Vital signs

Changes in blood pressure and other vital signs will be summarized by baseline quartile.

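### Blood pressure and heart rate from unscheduled visits feed no worst-value table by arm, although laboratory results do; QTcF has no maximum post-baseline row

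*SAP*

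**What the plan says.** - **Collection.** Protocol 9.7 lists weight gain, adverse events and dose de-escalation among the reasons for an unscheduled visit, and continues: "At a minimum, unscheduled visits should include collection of adverse events, clinical chemistry, hematology, concomitant medications and vital signs". ECG is not in that minimum set.
- **Vital-sign tables.** SAP 12.5: "Actual values and changes from baseline values for vital signs and weight will be summarized descriptively by treatment group at all scheduled study visits". SAP 12.5.1 adds: "Changes in blood pressure and other vital signs will be summarized by baseline quartile". SAP 12.3.2 adds by-visit line plots of vital signs and ECG.
- **Which reading counts.** Under SAP 5.2.2, post-baseline non-laboratory values "are defined as the measurements collected on the day closest to" the target day. Ties go to the earlier reading and same-day readings are averaged. The laboratory rule in SAP 5.2.1 is explicit about unscheduled results: "Post-baseline laboratory measurements are defined as the scheduled or unscheduled measurements collected closest to (or on) the" target day. SAP 5.2.2 has no such words, and SAP 5.3, on unscheduled tests, deals only with repeated walk tests.
- **Laboratory worst case.** SAP 12.3.3: "Shift tables will not be limited to results collected at scheduled visits, but will use all available results".
- **QTcF.** SAP 12.4: "A summary table of the actual values and change from baseline will be presented for QTcF by treatment group". The categories of value and of change "will be summarized by visit and treatment group".
- **General commitment.** SAP 12.1 commits the safety analyses to every result obtained between randomization and study end. SAP 5.2 sends all measurements to listings.

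**The concern.** Unscheduled visits are largely those made because something may be wrong. The protocol treats early fluid overload as a known risk (5.1.2) and builds an unscheduled visit around rapid weight gain (9.1.1). Blood pressure and heart rate taken then are among the most informative vital signs in the trial. Yet the vital-sign tables are organised by scheduled visit, and no table takes each patient's highest or lowest value. For laboratory tests the same SAP does exactly that, using every result.

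Change from baseline in vital signs and ECG is a stated safety endpoint (Protocol 6.2.4). What is at stake is whether the report can compare by arm the number of patients who had an extreme blood pressure or heart rate between scheduled visits.

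**Working it through.** The documents give no figure on this point, so there is none to reproduce. The question is how often an unscheduled reading could be the value kept for a visit window.

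**Inputs.** Target days 7, 14, 28, 42, 56, 112 and 168, and the windows around them (SAP Appendix D, Table D 1). Scheduled visits within ±3 days of target (Protocol Table 3). Nearest-day rule (SAP 5.2.2). Assumptions: every scheduled visit is attended in window, and unscheduled readings may fill a window.

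**Days on which an unscheduled reading can be kept.** It must be at least as near the target as the scheduled reading, hence within 3 days of it.
- First six targets: 6 × 7 = 42 days.
- Day 168, counting only to Day 168: Days 165 to 168 = 4 days.
- Total: 42 + 4 = 46. Remaining: 168 − 46 = 122, and 122/168 = 73%.

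**Two-value Week 24 average.** Footnote b to Table D 1 averages the two values nearest the Week 24 target and does not say that this is for the walk test only. Vital signs are scheduled once in that window. Read literally, an unscheduled reading anywhere in Days 140 to 168 (29 days) could be the second value. Eligible days become 42 + 29 = 71. Remaining: 168 − 71 = 97, and 97/168 = 58%.

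**Share missing the by-visit table.** The counts above treat every day within 3 days of target as usable. The share for one unscheduled reading on a random day depends on where the scheduled visit falls (single Week 24 value):

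| Scheduled visits | Days 2–168 | Days 2–56 |
|---|---|---|
| all on target | 1 − 7/167 = 96% | 1 − 5/55 = 91% |
| uniform within ±3 days | 84% | 66% |
| all 3 days late (most favourable) | 1 − 46/167 = 72.5% | 1 − 32/55 = 42% |

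For the middle row, the chances of being kept at offsets −3 to +3 are 2/7, 4/7, 6/7, 7/7, 5/7, 3/7 and 1/7. They sum to 28/7 = 4 days per full target, and to 19/7 = 2.71 for a target cut off at its own day. Over Days 2–168: (6 × 4 + 2.71)/167 = 16% kept. Over Days 2–56: (4 × 4 + 2.71)/55 = 34% kept.

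If SAP 5.2.2 and 12.5 admit scheduled readings only, the share missing is 100%.

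**QTcF.** The only scheduled on-treatment ECG is at Week 24 or end of treatment (Protocol Table 3). Days 2 to 139, that is 138 of 167 days (83%), lie in windows with no scheduled ECG. With visits uniform within ±3 days, (138 + 2.71)/167 = 84% of unscheduled ECGs would reach a visit row if unscheduled readings are allowed, and none if they are not. An early terminator's ECG is placed by date (SAP 5.2.3), so before the Week 24 window it sits in an earlier row.

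**The case against.** The strongest reply is that little is truly hidden. Every reading is listed. SAP section 5 gives the minimum and maximum with each continuous summary, so a visit row is more than a mean. Unscheduled visits collect adverse events, an unfavourable sign can be an adverse event (Protocol 11.2.1.1), and treatment-emergent events are tabulated by arm. The DSMB reviews unblinded safety data quarterly. The endpoint is change from baseline, which SAP 12.4 and 12.5 deliver, and no document promises a worst-case vital-sign table.

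Much of this stands, and it limits the point. It does not remove it. A listing gives no count by arm. A visit maximum is one number per arm and covers only the readings kept for that visit. The adverse event route is partial: Protocol 11.6 says that once a diagnosis is recorded, accompanying signs are not entered separately, so a blood-pressure excursion within a fluid-overload event need not be tabulated. Laboratory results have the same route and still get worst-case tables.

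Three stronger readings are tempting, and the documents do not support them:
- **That unscheduled ECGs mostly reach no table.** ECG is not required at unscheduled visits. One taken before the Week 24 window would usually be alone in its window and so reach a visit row, unless unscheduled readings are barred, which SAP 5.2.2 does not say.
- **That 73% is a floor.** It assumes attended, in-window visits. If a scheduled visit is missed, the unscheduled reading may become the kept value, and footnote b alone brings the figure to 58%.
- **That an arm difference in extremes could not be seen at all.** Visit minima and maxima, QTcF categories, line plots and adverse event tables each show part of it.

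**Conclusion.** The point holds as a cheap improvement. Most blood-pressure and heart-rate readings from unscheduled visits would enter no by-arm vital-sign summary and would appear only in listings unless recorded as adverse events.

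With scheduled visits attended within ±3 days, such a reading cannot enter a by-visit table on about 122 of 168 days (73%), or 97 days (58%) under the two-value Week 24 average. Missed visits lower this. Over the first 8 weeks, when visits are closer together, the share is 66% with visits spread evenly within ±3 days, and can fall to 42% in the most favourable case. It is 100% if only scheduled readings are eligible, which the SAP leaves unclear.

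SAP 12.5 does not carry out the commitment in SAP 12.1 and departs from the laboratory practice in SAP 12.3.3. For QTcF the point is narrower: there is no maximum post-baseline row, so a patient's highest value is not gathered in one place.

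**What to change.** - **SAP 12.5:** add a worst post-baseline table by arm, with the highest and lowest systolic pressure, diastolic pressure and heart rate per patient from all scheduled and unscheduled readings. Add counts beyond stated descriptive cut-offs for blood pressure. The protocol's screening limits (systolic below 90 or above 160 mm Hg, diastolic above 100 mm Hg; exclusion criteria 7 and 8) may serve, labelled as screening limits and not as on-treatment safety thresholds.
- **SAP 12.4:** add a maximum post-baseline QTcF row using the categories already listed.
- **SAP 5.2.2:** state whether unscheduled readings may fill a window. In Appendix D, state whether the two-value Week 24 average applies to vital signs.
- **Period:** do not end it at the last dose. Under Protocol 9.1.1, patients with the specified weight gain in the first 8 weeks stop drug and are then examined, so the reading can follow the last dose. The off-treatment windows begin only 7 days after it (Table D 2). The SAP's own treatment-emergent period, to 30 days after the last dose, would cover the gap.

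**Cost:** one table and one row from data already collected. The downside is that an arm with more unscheduled visits has more chances of an extreme value, so the number of readings per arm should stand beside the counts.

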12.5.1. Vital signs

Changes in blood pressure and other vital signs will be summarized by baseline quartile.

12.5.2. Weight

Weight change from baseline will be summarized by baseline BMI category (< 18.5, 18.5 to < 25.0, 25.0 to < 30.0, 30.0 or greater).

13. PHARMACOKINETIC ANALYSES

The planned pharmacokinetic analyses are described in a separate document.

14. PROTOCOL DEVIATIONS

The Principal Investigator (PI) or designee must document any protocol deviation or violation and report them to the appropriate Institutional Review Board (IRB), Ethical Committee (EC), or Research Ethics Board (REB). The PI must follow the applicable IRB, EC, or REB guidelines.

If there is an immediate hazard to a patient, the PI may deviate from the protocol without prior Sponsor and IRB, EC, or REB approval. Notification to Reata, the IRB, EC, or REB is necessary for the deviation.

14.1. Major protocol deviations

Major protocol deviations from entry criteria and treatment compliance will be listed.

14.2. Other protocol deviations

Protocol deviations that are not major are termed “other” will not be listed but will be included in the analysis data.

15. OTHER TOPICS

15.1. Analysis by study site

Because the number of patients at each site is likely to be small, no analyses will be performed by study site.

15.2. Interim analysis

A DSMB will be reviewing data from the study to ensure patient safety. The DSMB charter describes the interim reviews of safety. No interim analyses for efficacy are planned.

15.3. Subgroups analysis

Safety and efficacy outcomes will be analyzed for the subgroups of interest listed below. The following subgroup analyses will be tabulated using summary statistics:

- Geographic region: US; non US
- Age by median (above and below equal median)
- Sex: female; male

- Race: White; Non-White
- Ethnicity: Non-Hispanic/Latino; Hispanic/Latino
- Number of PAH medications at baseline: 0-1; 2
- CTD type: scleroderma; no scleroderma
- Baseline FC: II; III
- Baseline 6MWT: < 450 m; \geq 450 m
- On ERA (PAH med): yes; no
- On PD5i (PAH med): yes; no
- Baseline Hb: < 10.5 g/dL; \geq 10.5 g/dL
- Baseline BMI: < 30; \geq 30
- End-of-treatment dose: 10 mg; <10 mg; placebo

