15. Serum aminotransferase (ALT or AST) levels > 1.5X the upper limit of normal (ULN) at Screening;
16. Hemoglobin (Hgb) concentration < 10.5 g/dL at Screening;
17. Diagnosis of Down syndrome;
18. History of malignancy within 5 years prior to Screening, with the exception of localized skin or cervical carcinomas;
19. Untreated or uncontrolled active bacterial, fungal, or viral infection;
20. Known or suspected active drug or alcohol abuse, per investigator judgment;
21. Use of inhaled nitric oxide within 7 days prior to Screening and Day 1 visits, excluding acute vasodilator testing during diagnostic cardiac catheterization;
22. Major surgery within 30 days prior to Day 1 or planned to occur during the course of the study;
23. Unwilling to practice acceptable methods of birth control (both males who have partners of childbearing potential and females of childbearing potential) during Screening, while taking study drug, and for at least 30 days after the last dose of study drug is ingested;
24. Women who are pregnant or breastfeeding;
25. Any disability or impairment that would prohibit performance of the 6MWT;
26. Any abnormal laboratory level that, in the opinion of the investigator, would put the patient at risk by trial enrollment;
27. Patient is, in the opinion of the investigator, unable to comply with the requirements of the study protocol or is unsuitable for the study for any reason;
28. Known hypersensitivity to any component of the study drug;

29. Unable to communicate or cooperate with the investigator because of language problems, poor mental development, or impaired cerebral function.
30. Patient has active myositis;
31. Use of total parenteral nutrition within one year of the Day 1 study visit;
32. History of acute renal crisis within one year of the Day 1 study visit;
33. Patient has participated in investigational trials where bardoxolone methyl was administered.

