9.1.7. Anemia

Anemia is a common occurrence in PAH patients. If a patient has serum levels of hemoglobin < 10.5 g/dL at Screening, the patient will be allowed to re-screen following anemia treatment. Re-screening can occur no sooner than 30 days following initiation of anemia treatment.

Patients with anemia who re-screen must repeat all Screening assessments at the re-screening. If the patient takes agents to treat anemia (including but not limited to supplemental iron, erythropoietin, or intravenous iron) the patient must remain on a stable dosage for at least 30 days prior to Day 1. If the patient receives intravenous iron therapy during Screening, the intravenous infusion must be performed at least 30 days prior to Day 1.

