9.10.2. Inclusion/Exclusion

Inclusion and exclusion criteria must be reviewed as indicated in [Table 3](#). Patients must meet all of the inclusion and none of the exclusion criteria for entry in the study. Investigators should contact the medical monitor with any questions regarding eligibility prior to randomizing the patient on Day 1.

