5.1. Definition of baseline

This section describes which measurements taken prior to first dose of study drug will be used to calculate baseline for each study parameter. No measurement collected after first dose will be used in the calculation of baseline. The collection date and time of the sample will be compared to the date and time of first dose. Should a patient never receive study drug, only measurements collected prior to randomization will be used in the calculation of baseline values.

In general, the baseline value for any laboratory or non-laboratory parameter will be calculated as the mean of data sampled up until and including Day 1, but not occurring after first dose of study drug, except in the following circumstances:

- Whenever specific visit results (i.e., Screening A, B, or Day 1) are indicated, the results will be used regardless of whether the measurements were collected within the protocol-specified window of time ([Appendix D](#)), as long as they precede first dose.
- For eligibility purposes, only two 6MWT observations (Screening B and Day 1 preferred to Screening A and Day 1) will be used to determine eligibility (must be within 15% of each other and at least 150 m). Patients not meeting the eligibility criteria are listed.
- As the covariate in the primary efficacy analysis, the screening 6MWT will be either the average of Screening A 6MWT and Screening B 6MWT or the single Screening A 6MWT result if Screening B did not occur.
- For the outcome in primary analysis, the Day 1 6MWT will be subtracted from the 6MWT observation at each followup time to give the change score.
- For discrete efficacy outcomes, [REDACTED], the latest assessment will be used for analysis purposes.
- If a scheduled measurement prior to first dose is repeated, baseline calculations will use only one result per scheduled measurement (i.e., either the original or repeated). The original value will be used, unless it is missing. The repeated value will only be used if the original value is missing, otherwise the repeated value will be ignored. The CSR will include listings of all repeated measurements collected prior to first dose, indicating whether they were included in the calculation of baseline.

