with the heterogeneous Toeplitz structure, the model will use a homogeneous Toeplitz structure. Finally, if the model using the homogeneous Toeplitz structure does not converge, the model will use a compound symmetry structure which assumes equal correlation for a patient's measurements, regardless of how far apart in time they were taken.

- The models will include the following covariates:
 - Time defined as a categorical variable (i.e., no restriction is imposed on the trajectory of the mean outcome over time) (VOBS)
 - Treatment group (GRP)
 - N_PAH_MEDS (stratification variable for number of background PAH therapies)
 - Screening 6MWT (SCR_6MWT)
 - Screening 6MWT by time interaction (VOBS * SCR_6MWT)
 - Day 1 hemoglobin (Hb)
 - Time by treatment group interaction (GRP * VOBS)

The MMRM, as defined above, uses the screening value of the 6MWT as a covariate and the baseline value of the 6MWT for the computation of the outcome (the change from baseline). This allows adjustment for the “baseline” value between groups while providing the ability to provide valid estimates of the placebo-adjusted treatment effect.

In the event the MMRM model with an unstructured covariance structure does not converge, the following covariance structures are substituted, in the order listed. Each subsequent covariance structure is used only if each previous covariance structure is used and no previous model converged.

1. Heterogeneous Toeplitz covariance structure (assuming different variances at each time point and that measurements taken closer together in time are more highly correlated than those taken farther apart).
2. Toeplitz covariance structure (assuming measurements taken closer together in time are more highly correlated than those taken farther apart).
3. First order auto-regressive [AR(1)] covariance structure (assuming measurements taken closer together in time are more highly correlated than those taken farther apart, but the correlation is more constrained than the Toeplitz structure).
4. Compound symmetry covariance structure (assuming equal correlation for measurements from a patient, regardless of how far apart in time they were taken). A compound symmetry covariance structure was assumed in the sample size calculation.

Results of MMRM are summarized in tables and line plots. Additionally, line plots of 6MWT change from baseline, labeled by treatment group up to and including Week 24 are generated

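### The hemoglobin subgroup in SAP 15.3 is cut at the entry limit of 10.5 g/dL, so its low row will hold few patients and is unlikely to support a useful comparison

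*SAP*

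**What the plan says.** - **The cut.** SAP 15.3 names subgroups for both safety and efficacy. The Hb entry sets "Baseline Hb: < 10.5 g/dL" against values at or above that limit. The subgroup results are descriptive tables; no test or interaction analysis is named.
- **The entry limit.** Protocol 8.2, exclusion 16, reads "Hemoglobin (Hgb) concentration < 10.5 g/dL at Screening". Protocol 9.10.2 adds: "Patients must meet all of the inclusion and none of the exclusion criteria for entry in the study".
- **Re-screening.** Protocol 9.1.7 says: "If a patient has serum levels of hemoglobin < 10.5 g/dL at Screening, the patient will be allowed to re-screen following anemia treatment". It continues: "Patients with anemia who re-screen must repeat all Screening assessments at the re-screening". The limit therefore applies a second time.
- **Baseline.** Under SAP 5.1 a baseline value in general "will be calculated as the mean of data sampled up until and including Day 1", before the first dose. Where a scheduled pre-dose measurement was repeated, "The original value will be used, unless it is missing".
- **The primary model.** SAP 11.1.1 adjusts for Hb measured on Day 1, not for the averaged baseline. It has no Hb-by-treatment term.

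**The concern.** A subgroup table is useful when both sides hold enough patients to compare the arms. Here the dividing line is the line that keeps patients out of the trial, so nearly all enrolled patients should lie on one side. The high row then restates the overall result. The low row may hold a handful of patients, possibly all in one arm.

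Hb is a covariate in the primary model, but that adjustment does not show whether the treatment effect changes with Hb. In the unredacted text, the subgroup table is the only place where that question would be looked at. With this cut it is unlikely to be answered.

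The SAP avoids very small groups elsewhere. It drops analyses by site because sites will be small (15.1), allows the two lower background-therapy strata to be merged if events are few (11.2), and pools the same two levels in the subgroup list (15.3).

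**Working it through.** There is no figure in the plan to reproduce: no subgroup size is given and the sample-size assumptions are redacted.

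**Step 1. Compare the limits.** Subgroup cut: 10.5 g/dL (SAP 15.3). Exclusion limit: 10.5 g/dL (Protocol 8.2). They are identical, and this needs no assumption.

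**Step 2. What a fall after Screening must do.** Take one Screening value S (at least 10.5) and a Day 1 value D. Baseline is (S + D)/2. It is below 10.5 only if D < 21 − S, which is a fall of more than 2 × (S − 10.5).
- S = 11.0: D must be below 10.0, a fall of more than 1.0 g/dL.
- S = 12.5: D must be below 8.5, a fall of more than 4.0 g/dL.

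**Step 3. Other routes to the low row.**
- A failing original value is kept over a passing repeat (SAP 5.1).
- Values from a failed first screening stay in the mean; the SAP does not say whether they drop out. For example, 9.8, 10.7 and 10.8 average 31.3/3 = 10.43, although Hb rose.
- An ineligible patient is enrolled. SAP 14.1 provides for listing major deviations from entry criteria.

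**Step 4. Likely share.** The Hb distribution is assumed, since no document gives one: true Hb normal with mean 11.5 to 13.5 and SD 1.4 to 1.5 g/dL; independent within-patient error with SD 0.4 to 0.8 at each visit; selection on Screening Hb of at least 10.5. Two million simulated patients per setting gave these shares below 10.5:

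| Assumed mean Hb (g/dL) | Mean of Screening and Day 1 | Day 1 alone |
|---|---|---|
| 11.5 | 2.9–5.4% | 6.4–12.7% |
| 12.0 | 1.9–3.6% | 4.3–8.9% |
| 12.5 | 1.1–2.2% | 2.6–6.0% |
| 13.0 | 0.6–1.3% | 1.5–3.8% |
| 13.5 | 0.3–0.7% | 0.7–2.2% |

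With the averaged baseline the range is 0.3% to 5.4%:
- N = 130: 0.003 × 130 ≈ 0.4, up to 0.054 × 130 ≈ 7 patients.
- N = 200: 0.003 × 200 ≈ 0.6, up to 0.054 × 200 ≈ 11 patients.

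These counts cover both arms together. The high row holds about 94.6% to 99.7% of patients. The simulation covers only a change between Screening and Day 1, not the routes in Step 3.

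**Step 5. What the low row can estimate.** Approximate 95% half-width for a difference in mean 6MWD change = 1.96 × SD × √(2/n per arm). The SD is assumed to be 40 to 70 m; the results below use 60 m.
- n = 1 per arm: 1.96 × 60 × √2 = 166 m.
- n = 3 per arm (near the upper end for N = 130): 1.96 × 60 × √(2/3) = 96 m.
- n = 8 per arm (top of the Day 1 range, 0.127 × 130 ≈ 16.5 patients): 1.96 × 60 × √(2/8) = 59 m.
- Median split at N = 130, 65 per side and 32.5 per arm: 1.96 × 60 × √(2/32.5) = 29 m, or 19 to 34 m over SDs of 40 to 70 m.

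**The case against.** The best defence has four parts.

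1. **The low row can be populated.** Protocol 9.1.7 calls anemia common in PAH, and treated, re-screened patients may cluster just above the limit. Step 3 adds routes that the simulation leaves out. This stands. It is why the range includes means down to 11.5 g/dL and why the shares are rough. Even so, the averaged baseline leaves the low row small at every setting tried.
2. **A small row can still inform.** SAP 15.3 covers safety, and a description of the few patients below the entry limit may be wanted. The SAP gives no reason for the cut, so this purpose can be neither confirmed nor ruled out. A listing would serve it as well.
3. **Little depends on it.** The tables are descriptive, carry no stated claim, and leave the primary analysis untouched. This stands and keeps the point minor.
4. **A median depends on the data, whereas 10.5 is the protocol's own limit.** This is fair as a matter of preference. Any cut inside the enrolled range would do, and a median fixed on blinded data does not depend on treatment results.

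A reader might go further and infer that only a patient whose Hb falls after Screening can land below 10.5, or that the subgroup can show nothing. The documents support neither. SAP 5.1 keeps an original value over a repeat, the fate of first-screening values is not stated, and eligibility deviations are foreseen. A few patients can also be described even if they cannot support a comparison of the arms.

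**Conclusion.** The point holds as a minor one. The subgroup cut and the Screening exclusion limit are the same number, which the documents show directly. The low row is therefore expected to be small, and the subgroup is unlikely to support a useful comparison by Hb.

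The size rests on an assumed Hb distribution. With the averaged baseline, about 0.3% to 5.4% of patients fall below 10.5 g/dL. The chance that none of 130 does is (1 − p)^130: about 0.7 at p = 0.3%, and below 0.001 at p = 5.4%. An empty row is thus possible but not certain. With the Day 1 value the share is about 0.7% to 13%, so the choice of Hb value matters. SAP 15.3 does not make that choice explicit: the general rule in SAP 5.1 points to the mean, while the primary model uses Day 1.

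The primary result and its error rate are unaffected.

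**What to change.** Before unblinding, amend the Hb line in SAP 15.3:

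- Replace 10.5 g/dL with a cut inside the enrolled range. The median of baseline Hb, taken from blinded data, is the simplest choice and matches the treatment of age in the same list.
- State whether the subgroup uses the averaged baseline of SAP 5.1 or the Day 1 value of the primary model.
- If patients below 10.5 g/dL are of interest in themselves, show them in a separate listing.

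The cost is an edit to one SAP entry. It needs no new data and no change to trial conduct, sample size or the primary analysis.
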